Since it has been shown by Foster GD et al. [24] that 86% of overweight and obese diabetic subjects have sleep apnea, we feel that, in addition to including subjects without sleep apnea, we should include patients with sleep apnea controlled on C-PAP. Both of these groups of patients will be protected from any additional hypoxia associated with sleep apnea that would add to the safe hypoxia generated by the tent, but including the group with sleep apnea controlled on C-PAP will allow us to enroll and complete the study which has only enrolled one patient in over a year when limiting those studied to those without sleep apnea.

HYPOTHESIS AND AIMS

Aim: To determine the effect of 2-week overnight sleep in moderate hypoxia on glucose tolerance in participants with type 2 diabetes.

Hypothesis: Exposure to moderate hypoxia (2400 m altitude) for 14 consecutive nights in obese, type 2 diabetic subjects will improve glucose tolerance

Primary endpoint: Results from the 75 g oral glucose tolerance test (OGTT) assessed by different statistical approaches including:

- Traditional area under the curve (glucose and insulin)
- Repeated measures mixed effect model
- Matsuda Index
- Kahn's calculation of indices of insulin sensitivity and insulin secretion

Exploratory endpoints: Fasting plasma fructosamine and hemoglobin A1-C as well as daily body weight

SUBJECTS

We plan to have n = 10 completers.

Inclusion criteria:

- Aged 20-65 yrs
- Have a BMI < 55 kg/m²
- Body weight 450 lbs or less

PBRC# 2015-018

- Have *either* been diagnosed with type 2 diabetes, or 125 mg/dl < Fasting Blood Sugar < 200 mg/dl, or hemoglobin A1-C \geq 6.5%
- Non-smokers
- Weight stable over the previous 3 months (< 3 kg fluctuation)
- Known diagnosis of sleep apnea and ownership of a continuous positive airway pressure (C-PAP) device that must be worn throughout the nights spent in the tent
- If no known presence of sleep apnea, be willing to spend one night in a sleep laboratory (Louisiana Sleep Foundation) to assess presence of sleep apnea

Exclusion criteria:

- Diagnosed with T2DM \geq 15 years ago
- Pregnant Women
- Current insulin treatment
- Treatment with sulfonylureas or glitinides
- Treatment with a GLP-1 agonist
- Any other diabetes medication other than an oral agent is exclusionary unless otherwise cleared by medical investigator.
- Chronic Obstructive Pulmonary Disease (COPD)
- Congestive heart failure

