Glucose tolerance will be assessed using an oral 75 g oral glucose tolerance test (OGTT). Subjects will be studied after an overnight fast. An intravenous line will be placed and one baseline sample will be drawn at -5 minutes. The subjects will then consume a 75 g glucose beverage within 5 minutes. Blood samples will be collected at 30, 60, 90, and 120 to measure serum glucose, insulin, and free fatty acid concentrations. Whole body insulin sensitivity will be calculated using the Matsuda insulin sensitivity index ($10,000/\sqrt{[\text{fasting glucose} \times \text{fasting insulin}] \times [\text{mean OGTT glucose} \times \text{mean OGTT insulin}]}$). We will also assess insulin secretion as described by [name]. In brief, the early insulin response during the OGTT, also known as the insulinogenic index is calculated as the ratio of the change in insulin to the change in glucose concentrations from 0 to 30 minutes. The oral disposition index (D_{lo}), a measure of b-cell function is calculated as $[\Delta \text{ insulin}_{0-30\text{min}} / \Delta \text{ glucose}_{0-30\text{min}}] \times 1/\text{fasting insulin}$. Complementary to the glucose response, we would also monitor the changes in the blood FFAs as a measure of the adipose tissue capability to suppress lipolysis in response to insulin. So, it can be used as a marker of insulin sensitivity in terms of adipose tissue. We will calculate the insulin sensitivity index for blood FFAs by the formula: ISI (ffa) = $2/(INSp \times FFAp) + 1$, where INSp and FFAp indicate insulinemic and blood FFA areas, respectively, of the person under study recorded during the OGTT.

DXA scan

Dual X-Ray absorptiometry (DXA) scans will be performed using the GE iDXA whole-body scanner to assess body composition. The protocol requires that participants lie on a table wearing a hospital gown and no metal containing objects, while the scanner emits low energy X-rays and a detector passes along the body. The scan takes 10 minutes and the radiation dose is less than 1 mrem, equal to about 12 hours of background radiation. Fat mass is calculated from weight (kg) on a scale and % body fat and fat-free mass by subtracting fat mass from total body weight (kg).

Sample size. This is a pilot study to test the impact of mild hypoxia in participants with type 2 diabetes. We therefore did not perform a power analysis.

Data analysis

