Data will be expressed as mean +/- SE. Values before and after exposure to hypoxia will be compared using the paired Student's t test or a Wilcoxon rank signed test. Despite the pilot nature of this study, the results may be published as a short communication depending on the potential changes in insulin sensitivity.

Data collection, storage and confidentiality

All results will be kept in locked file cabinets and restricted-access computers. All of these will be kept separate from records with names and other personal information. The only people who

PBRC# 2015-018

will know that these patients are research participants are members of the research team. No information about them, or provided by them during the research, will be disclosed to others without their written permission, except if it is necessary to protect their rights or welfare (for example, in case of injury or emergency care), or if it is required by law. When the results of the research are published or discussed in conferences, no information will be included that would reveal the identity of these patients. Participants will be identified by codes when the data gathered in this procedure is presented or published. Authorized representatives of the National Institutes of Health may need to review records of individual participants. As a result, they may see their name; but they are bound by rules of confidentiality not to reveal the patients' identity to others.

RISK/BENEFIT ASSESSMENT

The known risks, inconveniences or side effects involved in this study are the following:

Procedure	Risk
EKG	There are no risks associated with this test. There is a small possibility there may be some redness or irritation if you happen to be allergic to the adhesive on the electrodes.
Body composition by DXA	The amount of radiation used for this procedure is very small. The radiation dose for this scan is equivalent to the radiation you are naturally exposed to in the environment in less than one day. Scans will not be performed on any subject who is pregnant, and all females should inform the DXA technologist if there is any possibility that they are pregnant.
Blood Draws	Bruising, bleeding, pain, infection. These will be minimized by using trained phlebotomists with sterile techniques.

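### ISI(ffa) as printed adds the pure number 1 to a quantity with unstated units, so its mean level and percent change have no fixed meaning

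*Combined protocol and SAP*

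**What the plan says.** Under Methods and Procedures, Oral glucose tolerance test, the FFA work is introduced as supporting: "Complementary to the glucose response, we would also monitor the changes in the blood FFAs". The index is then given as "ISI (ffa) = $2/(INSp \times FFAp) + 1$, where INSp and FFAp indicate insulinemic and blood FFA areas", and these areas are described as "respectively, of the person under study recorded during the OGTT". The section states no unit for insulin, FFA or the time axis of the areas. It divides by no reference value and cites no source for this index.

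On sampling, the section says "one baseline sample will be drawn at -5 minutes" and then "Blood samples will be collected at 30, 60, 90, and 120 to measure serum glucose, insulin, and free fatty acid concentrations".

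The Data analysis section applies to every measure without exception: "Data will be expressed as mean +/- SE". It continues: "Values before and after exposure to hypoxia will be compared using the paired Student's t test or a Wilcoxon rank signed test".

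The Hypothesis and Aims section names neither this index nor FFA among its primary or exploratory endpoints. The only analyte concentration unit in the documents is mg/dl, for fasting blood sugar in the inclusion criteria.

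**The concern.** A sum makes sense only if both terms have the same dimension. Here 2/(INSp × FFAp) has the dimension of one over an insulin area times an FFA area, and 1 has none. The result depends on how large the first term happens to be next to 1, which depends only on the units the analyst picks. Under some choices the index is 1 plus a negligible remainder. Under others the 1 is the smaller part.

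What is at stake is the descriptive result. Two analysts could follow the protocol on the same data and report different means and very different percent changes. The Data analysis section does not itself prescribe percent change. However, the Data Safety Monitoring Plan section describes the earlier study in participants with obesity as a 20% improvement in insulin sensitivity, so readers may well want a percentage here too.

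**Working it through.** **Inputs from the protocol.** The formula, area definitions and sampling times come from the Oral glucose tolerance test section, the mean ± SE and paired tests from Data analysis, and the 10 completers from Subjects. The protocol states no value of the index, so there is no figure to reproduce.

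**Assumptions (not in the protocol).** Areas of 6,000 µU·min/mL and 40 mmol·min/L; 1 µU/mL = 6 pmol/L; a 20% fall in the product for illustration.

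**1. Algebra (no assumptions).** Let X = INSp × FFAp, and let a change of units multiply X by c. The printed index goes from 1 + 2/X to 1 + 2/(cX).
- The ratio of new to old values depends on X, so no single multiplier converts them.
- The excess over 1 is divided by exactly c. Values can therefore be converted by shift and scale once the units are known.
- The SE is divided by c, because the constant drops out. The mean becomes 1 + mean(2/X)/c. Percent change and coefficient of variation have a numerator that rescales and a denominator that does not, so both change.
- In a paired difference the 1 cancels and 1/c is a common factor. The t statistic and the signed ranks are unchanged.

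**2. One assumed participant.** 6,000 µU·min/mL ÷ 60 = 100 µU·h/mL = 600 pmol·h/L = 0.6 nmol·h/L, and 40 mmol·min/L ÷ 60 = 0.667 mmol·h/L.

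| Units | X | 2/X + 1 | Same, at 0.8X | Change |
|---|---|---|---|---|
| µU·min/mL × mmol·min/L | 240,000 | 1.0000083 | 1.0000104 | 0.0002% |
| µU·h/mL × mmol·h/L | 66.7 | 1.0300 | 1.0375 | 0.73% |
| nmol·h/L × mmol·h/L | 0.40 | 6.00 | 7.25 | 20.8% |

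From the second row to the third the multiplier is 6.00/1.03 = 5.83 at X but 7.25/1.0375 = 6.99 at 0.8X. The excess over 1 scales by 5.00/0.0300 = 6.25/0.0375 = 166.7 at both. Without the added 1, the change is 1/0.8 − 1 = 25% in every row.

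**3. Ten assumed participants.** One simulated set of before and after profiles (mean insulin 15 to 85 µU/mL, mean FFA falling from 0.6 to 0.2 mmol/L, trapezoidal areas over 0–120 min) gives, in the same three unit systems:
- baseline mean (SE): 1.0000054 (0.00000056), 1.0195 (0.00201) and 4.254 (0.335);
- change as a percentage of the baseline mean: 0.0001%, 0.37% and 14.7%;
- paired t = 1.715 and Wilcoxon p = 0.160 in all three.

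The last two SEs differ by 0.335/0.00201 = 167, the unit factor apart from rounding.

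**4. If the 1 belongs inside the denominator.** With raw areas, 2/(X + 1) gives 2/240,001 = 0.0000083, 2/67.7 = 0.0296 and 2/1.40 = 1.43 for the participant in step 2, so the level still depends on units. The test can now depend on them too. In the set of ten, across the unit systems tried, t runs from 1.715 to 2.051 and the Wilcoxon p is 0.160 or 0.105.

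**5. Log scale.** log(cX₁) − log(cX₀) = log X₁ − log X₀. The illustrative participant has a ratio of 0.80 in every unit system.

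**The case against.** **Inference is untouched.** A reader might infer that the significance test depends on the units. For the formula as printed it does not (step 1), and nothing stated in the protocol is miscalculated. This stands, and it confines the point to reporting.

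**The SE is not meaningless.** It rescales by one factor, as for any measured quantity, and stated units would make the values convertible. This stands too. Unstated units are also not peculiar to this index: the Matsuda, insulinogenic and disposition formulas give none. Those three, however, rescale by a single factor, so their percent changes do not depend on units. The added 1 removes that property here.

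**Minute-based units do not always flatten the index to 1.00.** Over assumed areas of 2,000–15,000 µU·min/mL and 15–80 mmol·min/L it runs from 1.0000017 to 1.0000667. With insulin in nmol/L the top is 2/(12 × 15) + 1 = 1.011, and with insulin in mU/mL it is 2/(2 × 15) + 1 = 1.067. The flattening depends on the concentration units as well.

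**The bracket may be a reading error.** The text was read from PDF, so the position of the 1 cannot be settled here. Step 4 shows that moving it does not cure raw areas. It would be wrong to present unit-dependent significance as a feature of the plan. Under that unconfirmed reading and an assumed 20% effect, simulated t-test significance differed between minute and nmol·h/L units in 14–27% of data sets. It differed in about 4–5% with no effect, and in 1–2% between minute and hour units with the effect.

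**Efficiency is a separate matter.** In simulations with assumed log-normal areas, 10 participants and a 20% lower product, paired t power was 0.110–0.324 as printed and 0.235–0.435 on the log scale. That loss comes from the reciprocal, not the units. The Wilcoxon test, which the plan also allows, was nearly unaffected (0.197–0.387 against 0.227–0.420). This is a secondary consideration only.

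**Conclusion.** The point holds as a minor error in a supporting index. As printed, the level, percent change and coefficient of variation of ISI(ffa) depend on a unit choice the protocol does not make. That follows from algebra alone. The sizes (1.000008, 1.030 or 6.00 for one participant; 0.0002%, 0.73% or 20.8% for one change) rest on the assumed areas, insulin conversion and 20% fall.

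A reader might go further and treat this as a flaw in the primary analysis, since the index comes from the OGTT and the list of primary approaches is worded as open. The documents do not support that: neither the index nor FFA is named there, and Methods calls the FFA work complementary. Nor do they show that the sponsor misplaced a bracket.

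**What to change.** Analyse the paired Day 14 minus Day 0 difference in log(INSp × FFAp). Use trapezoidal areas over 0–120 min with the −5 min sample as time 0, and report the result as a ratio of geometric means with a 95% interval. A ratio below 1 indicates higher sensitivity. This needs no units and no reference value.

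If the named index is reported as well, first check the bracket and any normalisation against the typeset protocol and the index's source. Then fix the units or reference values before analysis.

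The change needs no new visits or draws. It assumes that the −5 min sample is assayed for FFA and insulin; the sentence on analytes mentions only the later samples, so this should be confirmed. It changes the measure, its scale and its summary, and makes this one measure an exception to mean ± SE. The main loss is that the ratio cannot be compared directly with published ISI(ffa) values.

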Eligible subjects without a previous sleep apnea diagnosis will undergo an extensive two-step sleep evaluation, involving a home sleep test as well as a monitored sleep test at the Louisiana Sleep Foundation, to identify the presence of sleep apnea as well as closely monitor and evaluate oxyhemoglobin saturation levels during a single night sleep at 2400 m in the hypoxic tent, respectively. Sleep data will be thoroughly evaluated and assessed on a subject-by-subject basis by the chief medical director of the Louisiana Sleep Foundation to ensure the upmost safety precautions are taken. Only those subjects who exemplify safe oxyhemoglobin saturation levels during both sleep evaluation tests will be allowed to enroll in the study.

Eligible subjects with previous sleep apnea diagnosis who possess a C-PAP device will be required to use the C-PAP device throughout the nights spent in the tent.

Adverse Event Reporting: Adverse event monitoring will occur at mid-intervention (Day 7) and post-intervention (Day 14) visits, and participants will be instructed to call the study coordinator ([name]) at the onset of any abnormal effects (headache, nausea, vomiting, dizziness) between visits.

Data Safety Monitoring Plan. Drs. [name] and [name] will be responsible for monitoring the data, assuring protocol compliance, and conducting safety reviews after completion of the first participants and then every 6 weeks. During the entire study, [name] will monitor adverse events and determine if they are attributed to the study procedures. If any of those adverse events are suspected to be related to study procedures, they will be immediately reported to the PI and the IRB.

Such study has already been conducted in 8 participants with obesity and identified a 20% improvement in insulin sensitivity.

Potential Benefits: There is no direct benefit to the volunteers but knowledge may be gained that will benefit others. Participants will, however, receive some information about their health.

Payment for Participation: If participant completes all 14 days of the study, they will receive \$350 for the time spent in the clinic. Conversely, if the participant completes the mid-intervention visit (Day 7) but does not complete the post-intervention visit (Day 14), the participant will receive \$175. And finally, if the participant enrolls in the study but does not complete the mid-intervention visit (Day 7) or beyond, the participant will receive \$50. This compensation is in line with all the other studies conducted at the Pennington Biomedical Research Center and will be mailed within 4 weeks of study completion.

Financial Obligations of the Subjects: None

Emergency Care and Compensation for Research-Related Injury: No form of compensation for medical treatment is available from the Pennington Biomedical Research Center. In the

PBRC# 2015-018

event of injury or medical illness resulting from the research procedures the research volunteer will be referred to a treatment facility. The Pennington Biomedical Research Center is a research facility and provides medical treatment only as part of research protocols. Should a volunteer require medical treatment, community physicians and hospitals must provide them to him/her.

PBRC# 2015-018

Re: Q150541 – Study Determination for the Proposed Study titled, “Effect of 2-Week Nightly Moderate Hypoxia On Glucose Tolerance In Individuals With Type 2 Diabetes”

Dated: April 7, 2015

Received: April 14, 2015

Dear [name]:

The Food and Drug Administration (FDA) has reviewed your submission, dated April 7, 2015, requesting a risk determination for the proposed study titled, “Effect of 2-Week Nightly Moderate Hypoxia On Glucose Tolerance In Individuals With Type 2 Diabetes”. FDA has determined that your proposed clinical investigation is a nonsignificant risk (NSR) device study because it does not meet the definition of a significant risk (SR) device under § 812.3(m) of the investigational device exemptions (IDE) regulation (21 CFR 812).

An IDE application is not required to be submitted to, or approved by, FDA for a NSR study. A NSR study is, however, subject to the abbreviated requirements described in § 812.2(b) of the IDE regulation. The abbreviated requirements stipulate that the sponsor of the investigation must label the device in accordance with § 812.5; obtain institutional review board approval of the investigation as a NSR study; ensure that each investigator obtains informed consent from each subject under the investigator's care; comply with the monitoring requirements of § 812.46; maintain records required under § 812.140(b)(4) and (5) and file the reports required under § 812.150(b)(1) through (3) and (5) through (10); and ensure that participating investigators maintain the records required by § 812.140(a)(3)(i) and file the reports required under § 812.150(a)(1), (2), (5) and (7).

Under the abbreviated IDE requirements, a sponsor must also comply with the prohibitions against promotion and other practices as identified in § 812.7. According to this section of the regulation, the sponsor of a NSR study, investigator, or any person acting for or on behalf of the sponsor or investigator is prohibited from promoting or test marketing the investigational device until after FDA has approved the device for commercial distribution; commercializing the device by charging a price greater than that necessary to recover the cost of manufacture, research, development, and handling; unduly prolonging the investigation; and representing the investigational device as being safe or effective for the purposes for which it is being investigated.

Page 2 – [name].

